## TEMPLATE FOR MINUTES OF MEETING

Summary								
Meeting Topic								
Date			From		To			
Location			Note Taker			Duration		
Study brief Title: Effects of Sand Treatment on Osteoarthritis								
Official Title: Effect of Monazite Sands in Patients with Osteoarthritis of the Knee								
Ethical committee Protocol No: 3.160.891 Unique Protocol ID: T015-M02-2019AF002								
Agenda								
Tin	me Topic							
	Attendee List					_	_	
#	Name				-	Present	Reason	n of Absence
1								
2								
Meeting Notes								
1								
2								
Action Items								
#	Task				Person Responsible			Due Date
1								
2								
Prepared By:								
Dat								
	viewed By:							
	Date

# 1. Type of study

A randomized, blind-control clinical trial with paired samples will be conducted. Patients who meet the diagnostic criteria proposed by NICE (2014) with approximately 150 patients who agree to participate in the study and sign the Free and Informed Consent Term (Appendix A) will be elected.

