## 2. Experimental Protocol

The study will be carried out on the beaches of Areia Preta de Guarapari (source of monazitic sands) and on the beach of Itapoã in Vila Velha (sand without radiation). Selected patients will have their knees fully covered with beach sand, properly analyzed for radioactivity and temperature, for 30 minutes on 2 mornings a week for a period of 1 (one) year.

Patients will be enrolled in relation to age, gender, weight, height and body mass index (BMI). An investigation / monitoring will be performed regarding the current use of medications for disease control and associated comorbidities.

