# 3. The size of the sample

The sample size of the patients was calculated considering the necessary amount of subjects to detect difference of at least 3 points in the pain perception through the visual analgesic scale (scale from 0 to 10), considering a significance level of 1% and test power of 95% in two-tailed hypothesis test, as well as the value of 4 for standard deviation (MATA et al., 2015). The sample was calculated in 126 patients and considering a sample loss around 20%, the number of subjects was 150, with 75 subjects in each sample (BENAZZI, FIGUEIREDO, BANASSI, 2010).

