#### 9. Intervention

Patients selected for the study will have their knee (s) affected by OA fully submerged in the beach sand 2 (two) times per week for 30 (thirty) minutes each session at the same location and at the same time of day.

The natural gamma (②) radiation doses of the monazite sands will be monitored in both groups through equipment that counts and accumulates the records for the desired time. In addition, the radiation measurements ② will be associated with the atmospheric and climatic measurements of each group. An interview with the patients will be performed initially (Appendix B), blood collected for analysis and applied to the Visual Analogue Scale (Annex C) and WOMAC (Annex D). The questionnaires as well as the blood collection for laboratory analysis will be repeated at the beginning of the study (day zero) and after 1, 2, 3, 6, 9 and 12 months for later analysis and comparison of the data.

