## 14. Statistical analysis

Statistical analysis will be performed in the SPSS program (Statistical Package for the Social Sciences, version 13.0). For the analysis, descriptive statistics will be performed, with measures of central tendency (mean, median and standard deviation), for variables that follow the normal distribution. Qualitative variables will be expressed in frequency and percentage. The difference will be analyzed by the chi-square test or Fischer test for the categorical variables and the Mann-Whitney and Student tests for the resulting variables. A statistically significant difference will be considered when p <0.05.

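### The trial is labelled as paired without saying what is paired; the primary test should be stated as a between-arm comparison of VAS adjusted for day-zero VAS

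*Combined protocol and SAP*

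**What the plan says.** All references are to the combined protocol and SAP.

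- **Section 1 (Type of study):** the study is described as a randomized "clinical trial with paired samples". No definition of the pairs follows, here or later.
- **Section 2 (Experimental Protocol):** there are two beaches, one with monazite sand and a comparator "on the beach of Itapoã in Vila Velha (sand without radiation"). The section also says "Patients will be enrolled in relation to age, gender, weight, height and body mass index (BMI"), without a matching procedure.
- **Section 3 (The size of the sample):** the trial is sized to "detect difference of at least 3 points in the pain perception", with SD 4, two-sided 1% significance and 95% power. This gives 126 patients, raised to 150 "with 75 subjects in each sample". No within-pair correlation is given, and the plan does not say whether 4 is the SD of scores, of change or of paired differences.
- **Section 9 (Intervention):** the questionnaires, VAS among them, are "repeated at the beginning of the study (day zero) and after 1, 2, 3, 6, 9 and 12 months".
- **Section 10.1 (Primary outcome Measure):** the outcome is change in VAS pain. No visit and no comparison between arms is named.
- **Section 14 (Statistical analysis):** chi-square or Fisher for categorical variables, and "the Mann-Whitney and Student tests for the resulting variables". There is no signed-rank test, McNemar test, explicitly paired t-test or covariate-adjusted model.

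**The concern.** The design label points to a paired analysis, while the sample size and every test whose type is clear point to two independent groups. The one test whose type is open, Student, is also the one that can be run either way. Because the primary outcome is described only as change, an analyst could test change from day zero separately in each arm and still claim to follow the plan.

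Such tests ask whether pain changed in each group. The trial exists to ask whether it changed more with monazite sand than with control sand. If both groups improve for reasons common to both, a significant result in one arm and a non-significant one in the other can easily be presented as benefit when the arms do not differ.

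A second, smaller matter goes with it. Day-zero VAS enters the planned tests only through the change score and not as a covariate, so precision that the collected data already offer is left unused.

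**Working it through.** **1. Reproduce the stated sample size.** Inputs from Section 3: difference 3, SD 4, two-sided alpha 0.01 (z = 2.576), power 0.95 (z = 1.645).

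- Two independent groups: n per arm = 2 × (2.576 + 1.645)² × (4/3)² = 63.34, total 126.7. This matches the stated 126 apart from rounding (rounding up gives 64 per arm, 128 in total).
- Paired formula, with 4 as the SD of differences: n = (2.576 + 1.645)² × (4/3)² = 31.7, so 32 pairs (36 with the t distribution).
- Paired formula, with 4 as the SD of a single score and within-pair correlation ρ, so that the SD of differences is 4 × √(2(1 − ρ)): 64 pairs at ρ = 0, 45 at ρ = 0.3 and 32 at ρ = 0.5. Only ρ = 0, which is no effective pairing, gives about 126 patients.

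The trial was therefore sized as two independent groups.

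**2. Size of the risk if within-arm tests were used.** Assumptions, not given in the documents: both arms have the same true mean change d, the SD of change is 4, and tests are two-sided at 5% (the Section 14 level). Arm sizes: 60 (150 × 0.8 / 2, after the stated loss) or 63 (126 / 2). For each arm, p is the chance of a significant before-after test, with non-centrality d√n/4. The chance that exactly one arm is significant is 2p(1 − p).

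| True change in both arms | p, n = 60 (paired t) | Exactly one arm, n = 60 | p, n = 63 (normal) | Exactly one arm, n = 63 |
|---|---|---|---|---|
| 1 point | 0.478 | 50% | 0.510 | 50% |
| 1.5 points | 0.815 | 30% | 0.845 | 26% |
| 2 points | 0.968 | 6% | 0.978 | 4% |

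By symmetry, half of each figure is significance in the monazite arm alone: about 25%, 13% to 15%, and 2% to 3%. In the same scenario a valid between-arm test at 5% would wrongly favour monazite in 2.5% of trials.

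**3. Gain from adjusting for day-zero VAS.** Let r be the correlation of day-zero with follow-up VAS (not given; assumed), with equal variance at both visits. In units of that variance:

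- unadjusted change: 2(1 − r)
- linear model with arm and day-zero VAS: 1 − r²
- relative reduction: 1 − (1 − r²)/(2(1 − r)) = (1 − r)/2

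| r | Change | Adjusted | Reduction |
|---|---|---|---|
| 0.3 | 1.40 | 0.91 | 35% |
| 0.5 | 1.00 | 0.75 | 25% |
| 0.7 | 0.60 | 0.51 | 15% |

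**The case against.** The strongest reply is that the sections can be reconciled. If measurements are paired within each patient and the resulting change is compared between two independent groups, then the label in Section 1, the 75 per group in Section 3 (with 4 read as the SD of change) and the tests in Section 14 all fit. In Section 14, Student stands beside Mann-Whitney, chi-square and Fisher, so the unpaired form is its natural reading. This stands: the documents do not confirm that reading, but they do not exclude it. A reader might infer that Section 1 and Section 3 contradict each other and that one must be wrong; the text supports only an undefined term.

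It is also fair to say that no section plans a within-arm test, and that the 50% figure is the ceiling of 2p(1 − p), reached because a 1-point change puts p near one half. The figure falls quickly with a larger common change, so it should be read only as part of the range.

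Two further stronger readings are tempting:

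- **That patients are matched between arms and the tests wrongly ignore it.** The Section 2 sentence on age, gender and body size can equally mean that these are recorded, and no matching procedure is described. Had there been matching, an independent-groups test would be conservative. Its true error at a nominal 5%, 2(1 − Φ(1.96/√(1 − ρ))), is 3.9%, 1.9% and 0.6% at assumed ρ of 0.1, 0.3 and 0.5, and with 63 pairs its power for 3 points stays above 98%.
- **That baseline VAS is not used.** A change score uses it. What is absent is its use as a covariate.

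**Conclusion.** The concern holds as an undefined term and an unstated primary contrast. The plan does not say what is paired, does not say which form of the Student test applies, and does not say that the primary test compares the arms. The sizing arithmetic shows that two independent groups were intended.

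The consequence is a risk that the wording leaves open, not an error already built into the analysis. Its size depends on a common improvement that the documents do not give: about 50% of trials with exactly one arm significant at 1 point, 26% to 30% at 1.5 points and 4% to 6% at 2 points, about half of these favouring monazite. These figures assume an SD of change of 4, 60 to 63 patients per arm and no difference between arms.

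Separately, adjusting for day-zero VAS would reduce the variance by 35%, 25% or 15% against unadjusted change at assumed correlations of 0.3, 0.5 or 0.7. That is an improvement in efficiency; unadjusted change is not invalid. Harm from ignored matching is not part of this point.

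**What to change.** **Section 1:** replace the reference to paired samples by *with two parallel groups and repeated measurements within each patient*. If patients are in fact matched, say so, describe how, and include the matching variables or a pair term in the model.

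**Section 14:** state that the primary test is the between-arm difference in VAS at one pre-stated visit, chosen from those in Section 9, from a linear model with arm and day-zero VAS as terms. State that before-after tests within an arm are descriptive and support no claim of efficacy.

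**Section 10.1:** name the same visit and the same between-arm comparison, so that outcome and test agree.

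**Cost:** wording only. Day-zero and follow-up VAS are already collected, no patients or visits are added, and the model can be fitted in the software named in Section 14. The visit should be fixed before any outcome data are examined.

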## 2. Experimental Protocol

The study will be carried out on the beaches of Areia Preta de Guarapari (source of monazitic sands) and on the beach of Itapoã in Vila Velha (sand without radiation). Selected patients will have their knees fully covered with beach sand, properly analyzed for radioactivity and temperature, for 30 minutes on 2 mornings a week for a period of 1 (one) year.

Patients will be enrolled in relation to age, gender, weight, height and body mass index (BMI). An investigation / monitoring will be performed regarding the current use of medications for disease control and associated comorbidities.

# 3. The size of the sample

The sample size of the patients was calculated considering the necessary amount of subjects to detect difference of at least 3 points in the pain perception through the visual analgesic scale (scale from 0 to 10), considering a significance level of 1% and test power of 95% in two-tailed hypothesis test, as well as the value of 4 for standard deviation (MATA et al., 2015). The sample was calculated in 126 patients and considering a sample loss around 20%, the number of subjects was 150, with 75 subjects in each sample (BENAZZI, FIGUEIREDO, BANASSI, 2010).

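### If around 20% of the 150 enrolled are lost, 120 remain, six short of the 126 required; 150 keeps 126 only up to a 16% loss (minor effect on power)

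*Combined protocol and SAP*

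**What the plan says.** Section 3 of the combined protocol and SAP bases the sample size on a 3-point difference in pain on a 0 to 10 scale, a standard deviation of 4, a 1% significance level, 95% power and a "two-tailed hypothesis test". It then gives the result and the allowance for loss together: "The sample was calculated in 126 patients and considering a sample loss around 20%, the number of subjects was 150". The split is equal, 75 per group. Neither the inflation formula nor the base of the 20% is given.

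Section 1 repeats the enrolment figure as "approximately 150 patients who agree to participate in the study".

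Section 14 names "the Mann-Whitney and Student tests for the resulting variables" and sets the threshold: "A statistically significant difference will be considered when p <0.05". It matters here only for judging how much power the shortfall costs.

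**The concern.** A loss allowance is meant to ensure that the required number is still there after the expected loss. Patients are lost from those enrolled, so the usual step is to divide the required number by one minus the loss fraction. The step from 126 to 150 looks instead like adding about 20% to 126, which covers a smaller loss than 20% of those enrolled.

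Loss is a real prospect. Section 2 asks for two sessions a week for a year, section 9 has assessments to month 12, and section 7 removes patients for knee surgery, joint infiltration, or intolerance of heat or other discomfort. If the trial ends with 120 patients, a reader of section 3 would conclude that retention was worse than planned, when a 20% loss of those enrolled produces exactly that number. Some power would also be lost.

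**Working it through.** **Inputs (section 3):** difference 3; SD 4; two-sided alpha 0.01; power 0.95; required number 126; loss around 20%; enrolled 150, 75 per group.

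**Assumptions not in the plan:** for the power figures, two independent groups, no data from lost patients and, unless stated, equal loss in both groups. The headcounts in steps 2 and 3 need only that loss is counted from those enrolled.

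**1. Reproducing 126.** For two equal independent groups, total N = 4 × (z for 1 − alpha/2 + z for power)² × SD² / difference².

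N = 4 × (2.5758 + 1.6449)² × 16/9 = 126.68.

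The plan's 126 is this figure rounded down. Section 1 speaks of paired samples, but a one-sample (paired) formula with the same inputs gives (4 × 4.2207/3)² = 31.7, which does not match. The independent-groups formula is therefore the one behind 126.

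**2. Reproducing 150.**
- Adding 20% to the number required: 126 × 1.2 = 151.2, close to 150.
- Dividing by the fraction retained: 126/0.8 = 157.5, so 158 (79 per group), not close to 150.
- Margin actually added: 150 − 126 = 24, which is 24/126 = 19.0% of those required and 24/150 = 16.0% of those enrolled.

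**3. What 150 leaves.**
- 20% loss: 150 × 0.8 = 120, or 60 per group; 126 − 120 = 6 short.
- Largest loss that still leaves 126: 1 − 126/150 = 16.0%.

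**4. Power.** By normal approximation, power = Φ(3 / (4 × √(2/n)) − z), with n per group and z = 2.5758 at two-sided 0.01.
- n = 63: 3 / (4 × √(2/63)) = 4.209; Φ(4.209 − 2.576) = 0.949.
- n = 60: 3 / (4 × √(2/60)) = 4.108; Φ(4.108 − 2.576) = 0.937.
- n = 60 at two-sided 0.05: Φ(4.108 − 1.960) = 0.984.

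| Patients analysed | Two-sided alpha | Normal | t-test |
|---|---|---|---|
| 126 (63 per group) | 0.01 | 94.9% | 94.3% |
| 120 (60 per group) | 0.01 | 93.7% | 93.0% |
| 120 (60 per group) | 0.05 | 98.4% | 98.3% |

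The loss step costs 1.2 points (normal) or 1.3 points (t-test) at the 1% level. Because 126.68 was rounded down, 126 is already just under 95% before any loss; 95% is reached at 128 patients (normal, 95.2%) or 132 (t-test, 95.3%).

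**5. Sensitivity at two-sided 0.01, 120 patients.**
- Unequal loss, for illustration 50 v 70 remaining: 93.0% (normal) or 92.2% (t-test).
- Mann-Whitney, with an assumed efficiency of 3/π = 0.955 for normal data and 60 per group: 92.5% (normal).

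Neither changes the picture.

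**The case against.** The strongest reply is that no stated sum is wrong. Section 3 does not give a base for the 20%. Taken on the number required, the expected loss is about 24 patients, and 150 − 24 = 126 exactly. The inputs are also approximate: the loss is only around 20%, and section 1 gives the enrolment as approximate too. This part stands: on that reading 150 is consistent, and the shortfall depends on counting loss from those enrolled. But that is the ordinary meaning of losing part of a sample, and nothing else in the documents points to the other base. The gap between 16% and 20% is also large for rounding. If the margin on 126 was meant, the sentence should say so.

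The second reply is that the consequence is close to nil. That also stands, which is why the point is minor and no change in enrolment is proposed. The headcount does not depend on alpha, so the 5% threshold in section 14 reduces what the shortfall costs but does not remove it.

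The third is that section 1 describes paired samples while the power figures use independent groups. The formula that reproduces 126 and the 75 per group support that choice, and the headcount is unaffected.

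**Conclusion.** The concern holds, as a minor point. With loss counted from those enrolled, 150 does not keep 126 patients at the 20% allowance the plan states: it leaves 120, six short, and keeps 126 only up to a 16% loss. Given equal loss, independent groups and no data from lost patients, power with 120 is 93.7% (normal) or 93.0% (t-test) against the 95% target at the 1% level, and about 98% at the 5% level. Confidence in the headcount is high. The trial's ability to detect a 3-point difference is barely affected; what needs correcting is what section 3 says the 150 will deliver.

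**What to change.** Keep 150 and replace the sentence in section 3 with one of these:

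- (a) *Enrolling 150 patients (75 per group) allows for the loss of up to 16% of those enrolled while keeping the 126 calculated, which gives about 94–95% power at two-sided alpha 0.01.*
- (b) *Enrolling 150 patients and losing about 20% of those enrolled leaves 120 (60 per group), which gives about 93–94% power at two-sided alpha 0.01 (about 98% at two-sided alpha 0.05), assuming equal loss in both groups.*

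Option (b) fits if 20% is the loss the sponsor really expects among those enrolled; option (a) fits if the 20% was meant as a margin on 126. The cost is one corrected sentence, with no extra patients and no change to section 14. The difference between the 1% level in section 3 and the 5% threshold in section 14 is a separate point that this change does not settle.

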# 4. Ethical issues

The ethical issues of submission to the Human Research Ethics Committee will be met.

The team responsible for patient follow-up and data collection will be properly trained and composed of specialists from different areas, including an Orthopedist and a Pharmacist, and academics from the Medicine, Nursing, Physiotherapy and Pharmacy Courses at Vila Velha University.

#### 5. Inclusion criteria

Will be included in the study:

- Patients who meet the NICE (2014) diagnostic criteria for Primary Knee Osteoarthritis.
- Age between 30 and 95 years.

#### 6. Exclusion Criteria

#### Patients with:

- History of previous knee surgery.
- History of fracture in the knee region.
- History of any secondary OA associated with any cystic arthropathy.
- Any treatment for the knee with methotrexate.
- History of hemorrhagic disorders.
- History of any infiltration of the knee during the previous 6 months (eg corticosteroids and hyaluronic acid).
- Morbid obesity.
- History of severe psychiatric disorders.
- History of skin cancer.

## 7. Removal criteria

Patients will be removed when:

- Undergoing knee surgery during the course of the research.
- Subjected to joint infiltration with corticoids or any other type and medication of intraarticular use.
- Heat intolerant or other discomfort during exposure to sand.

For evaluation and follow-up of the volunteers will be carried out in parallel a work of pharmaceutical attention with monitoring of the use and frequency of medications, especially the use of analgesics and / or anti-inflammatories.

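### Section 7 removes randomised patients after knee surgery, joint injection or discomfort in the sand, and nothing keeps them in follow-up or analysis, so the VAS comparison is open to bias of unknown direction and size

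*Combined protocol and SAP*

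**What the plan says.** Section 1 of the combined protocol and SAP describes the design: "A randomized, blind-control clinical trial with paired samples will be conducted". Section 7 opens with "Patients will be removed when" and lists three triggers:

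- an operation on the knee while on study, worded as "Undergoing knee surgery during the course of the research";
- an injection into the joint, worded as "Subjected to joint infiltration with corticoids or any other type and medication of intraarticular use";
- intolerance of the sessions themselves, worded as "Heat intolerant or other discomfort during exposure to sand".

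All three are on-study events. Injection in the six months before entry is a separate exclusion in Section 6.

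Section 9 says that questionnaires and blood collection "will be repeated at the beginning of the study (day zero) and after 1, 2, 3, 6, 9 and 12 months". It does not say whether a removed patient stays on that schedule. Section 14 names "the Mann-Whitney and Student tests for the resulting variables" and a 5% threshold. It gives no analysis population, no missing-data method and no rule for scores after injection or surgery. Section 3 enlarges the sample, "considering a sample loss around 20" percent, without saying what makes up that loss. The pharmaceutical follow-up in Sections 7 and 13.3 monitors medication and does not keep removed patients in VAS follow-up.

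**The concern.** Randomisation makes the arms comparable as allocated. Section 7 takes patients out for events that occur later and may depend on outcome or treatment. Surgery and injection can be responses to uncontrolled knee pain, and Section 10.1 makes pain the primary outcome. Discomfort in the sand comes from the assigned exposure, and Section 2 places the two sands on different beaches, so these removals need not balance.

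If removed patients leave the VAS comparison, the result favours whichever arm loses more of its worse patients. The documents do not show which arm that would be. The allowance for loss protects power but does not restore comparability. If the term is left undefined, who counts could also be settled after outcomes are known.

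**Working it through.** **The plan's own figure.** Section 3 gives a difference of 3 points, SD 4, two-sided 1% and power 95%. Per arm, n = 2 × [4 × (2.576 + 1.645) / 3]² = 63.3, or 126.7 in total, which agrees with the stated 126. The step to 150 is close to 126 × 1.2 = 151.2; as a loss from 150 it allows (150 − 126)/150 = 16%. A full 20% loss from 75 per arm leaves 60 per arm. A t-test for 3 points then still has 93.0% power at the 1% level and 98.3% at 5%. Power is therefore largely protected, and the exposure is to bias.

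**Bias formula.** Let p be the share removed in an arm and g the mean VAS of removed minus retained patients, with higher VAS worse. The all-randomised mean equals the retained mean plus p × g, so the retained mean is too low by p × g. The retained-only difference, monazite minus control, is therefore off by

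bias = p(control) × g(control) − p(monazite) × g(monazite).

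**Assumptions, not in the documents.** The values of p and g; no true effect on all-randomised means. SD 4 and 75 per arm before removal are from Section 3, and the two-sided 5% level is from Section 14. Rejection rates come from the noncentral t distribution with the retained numbers, about 75 × (1 − p) per arm.

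| Removed (one arm vs other) | Retained | Gap g | Size of bias (points) | Type I error |
|---|---|---|---|---|
| 10% vs 20% | 68 vs 60 | 1, both arms | 0.1 | 5.2% |
| 10% vs 20% | 68 vs 60 | 2, both arms | 0.2 | 5.9% |
| 10% vs 20% | 68 vs 60 | 3, both arms | 0.3 | 7.0% |
| 10% vs 30% | 68 vs 52 | 1, both arms | 0.2 | 5.8% |
| 10% vs 30% | 68 vs 52 | 2, both arms | 0.4 | 8.4% |
| 10% vs 30% | 68 vs 52 | 3, both arms | 0.6 | 12.7% |
| Equal | equal | equal | 0 | 5.0% |
| 10% vs 10% | 68 vs 68 | 1 to 3 in one arm, 0 in the other | 0.1 to 0.3 | 5.2% to 7.2% |
| 20% vs 20% | 60 vs 60 | 1 to 3 in one arm, 0 in the other | 0.2 to 0.6 | 5.9% to 12.9% |

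Worked example, 10% removed on monazite and 30% on control, gap 3: bias = 0.30 × 3 − 0.10 × 3 = +0.6. The standard error is 4 × √(1/68 + 1/52) = 0.737, so the noncentrality is 0.81. Of all results, 12.5% are significant in favour of the control sand and 0.3% in favour of monazite. Swapping the rates mirrors this.

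Gaps of opposite sign widen the range. With 20% removed in each arm and gaps anywhere from −3 to +3, the bias lies between −1.2 and +1.2 points.

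**The case against.** The strongest point is that *removed* is undefined. It could mean from the sand sessions only, which suits the discomfort trigger, and the Section 9 schedule is not made conditional on continuing sessions. The consent form (Appendix A) is not in the text reviewed and might address withdrawal. This makes the bias conditional on a reading. It does not clear the plan: nothing in Sections 7, 9 or 14 says that removed patients continue, and Section 14 names no analysis set on either reading.

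Second, the sizes are modest and assumed. A bias of 0.1 to 0.6 points is 3% to 20% of the 3-point target. The 12.7% case has an average removal of 20%, the plan's whole loss allowance before ordinary dropout. It also needs removed patients, including those leaving only for heat, to average 3 points worse. At the 1% level of Section 3 the same case gives about 3.8%. These points stand as limits on the illustration. They do not exclude the larger values, because the documents give no removal rates.

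Third, Section 10.1 fixes no time point for VAS change, and an earlier one would lose fewer patients. This is also true: the figures describe whatever time point has the assumed removal.

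**Conclusion.** The concern holds. As naturally read, the plan conditions a randomised comparison on events after allocation that can depend on pain or on the assigned sand, and no section provides for follow-up or analysis of the patients concerned. Bias is possible, not certain, and its direction cannot be derived from the documents. With gaps of 1 to 3 points in the same direction in both arms and removal differing by 10 to 20 percentage points, it is 0.1 to 0.6 VAS points, with a nominal 5% error of 5.2% to 12.7%. It is zero when removal and gaps match, and can reach 1.2 points in either direction if gaps of up to 3 points differ in sign at 20% removal per arm. All of this assumes SD 4 and removal rates and gaps that the plan does not supply. The point should be fixed: the correction is cheap, and VAS scores not collected after removal cannot be recovered by later analysis.

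**What to change.** Leave the triggers for stopping sand sessions as they are.

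- **Section 7:** define *removed* as removed from sand sessions only. Patients who meet a trigger stay in the study for VAS, WOMAC and medication assessments at every remaining visit to month 12. Record the date and reason, and report them by arm.
- **Section 14:** state that the primary analysis includes all randomised patients in their assigned arm. Fix in advance how scores after injection or surgery, and missing scores, are handled.
- **Sensitivity analyses:** pre-state them, for example excluding scores after injection or surgery, or counting such patients as having no improvement. Another rule is acceptable if it is fixed before the data are analysed. The essentials are continued collection and a stated rule.

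**Cost.** Wording in two sections, plus questionnaires. If 10% to 20% of 150 patients were removed (assumed), that is 15 to 30 patients with at most 6 post-baseline visits each, so at most 90 to 180 questionnaire visits.

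**Downside.** Scores after injection or surgery may dilute a difference between arms. If 10% versus 20% of patients had such treatment and it lowered VAS by 1 to 3 points (assumed), the dilution is (0.20 − 0.10) × 1 to 3 = 0.1 to 0.3 points. Cutting a 3-point effect to 2.7 lowers power at 63 per arm from 98.7% to 96.4% at the 5% level, or from 94.3% to 87.7% at 1%. This is cautious: with all 75 per arm analysed, power at 2.7 points is 98.4% and 93.5%. If the arm doing better had more such treatment, the difference would be enlarged instead, which is a further reason to report these events by arm.
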